Aim 1: Determine whether interdisciplinary outpatient palliative care for PD and APD improves patient quality of life (QOL) and caregiver burden as compared to usual care including a neurologist. We will randomize 300 PD and APD patients from 3 sites who are at high risk for poor outcomes in a 1:1 ratio to either: a) Usual care or b) Usual care augmented by an outpatient interdisciplinary palliative care team. Data regarding patient symptoms, QOL and caregiver burden will be measured at baseline, 3, 6, 9 and 12 months. Our primary outcomes will be differences between groups in patient QOL and caregiver burden at 6 months. We will also examine patient symptom burden, spiritual wellbeing and mood as planned secondary outcomes. We *predict* that patient QOL and caregiver burden will be significantly improved in the palliative care group versus usual care at 6 months and that this difference will persist and widen by 12 months.

Aim 2: Describe the effects of an interdisciplinary outpatient palliative care intervention on patient and caregiver costs and service utilization. Data regarding health-related costs, including informal caregiver time, and the use of health and social services for the three months prior to each study visit will be assessed for all participants from Aim 1 using a standard schedule. Our primary outcome will be the difference between groups in total patients and caregiver costs from month 0 to month 6 of the study. Secondary analyses will

examine changes in healthcare utilization and cost from a systems perspective. We *predict* patient/caregiver costs will be lower for the palliative care group versus usual care at 6 months and that service utilization will shift towards home services and away from acute care such as emergency room visits and hospitalizations.

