Aim 1: Determine whether interdisciplinary outpatient palliative care for PD improves patient quality of life (QOL) and/or caregiver burden versus usual care including a neurologist.

Rationale and Design: The objective of this Aim is to provide the first comparative effectiveness data on whether augmenting usual care with interdisciplinary outpatient palliative care improves patient QOL and/or caregiver burden in patients at high risk for poor outcomes. Given the unmet needs facing this population there are great potential benefits from incorporation of this approach. Although it may seem obvious that more care would be better than less, several multidisciplinary interventions in PD and palliative care have failed to meet their primary endpoints in randomized trials and thus could present an additional burden to patients and caregivers in terms of time, cost and emotional investment.^{44, 45} We will randomize 300 PD patients from 3 sites who are at high risk for poor outcomes in a 1:1 ratio to either: a) Usual care including a neurologist or b) Usual care augmented by an outpatient interdisciplinary palliative care team. Data regarding patient quality of life, symptom burden and caregiver distress will be measured at baseline, 3, 6, 9 and 12 months. Our primary outcomes will be differences between groups in patient symptom burden and caregiver burden at 6 months. This time point was chosen to capture both early effects of the intervention as well as probable measurable decline in control arm. We will examine symptom burden, spiritual wellbeing and mood as planned secondary outcomes. We *predict* that patient QOL and caregiver burden will be significantly improved in the palliative care group versus usual care at 6 months and that this difference will persist at 12 months.

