The outcomes will be modeled with mixed regression model analysis, with correlation for repeated measures, at baseline and at 3, 6, 9, and 12 months. The empirical covariance estimator may be used to safeguard against model misspecification. The models will control for time, interaction between treatment and time, and potential baseline confounders, including gender, age, depression, and disease severity. The default model will have linear time trajectories for each treatment group, and linear functions for baseline controlling covariates. The linearity assumptions will be checked. Non-linear functions could be approximated with piecewise linear functions or transforms. The main contrasts will be the difference in areas under the fixed effect change from baseline curves for the palliative and treatment control groups, and the mean difference in change between 6 months and baseline between the groups. Secondary tests will be conducted for the mean difference in change from baseline between the groups at the 3, 9, and 12-month time points. The contrasts, controlled for all covariates, will be tested for significance using T-tests and F-tests, with an alpha level of 0.05. The effect estimates, 95% confidence intervals, and p values will be reported. In the process, the interaction between time and treatment will be tested. If the time trajectories are linear, then all tests are stochastically equivalent to the time by treatment interaction test with one parameter. Binary outcomes and count outcomes will be analyzed with logistic regression and Poisson regression respectively. Generalized mixed models will account for repeated measures. We plan to perform subgroup analyses for patients with dementia, severe disease, and depression and may perform exploratory subgroup analyses depending on primary results.

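### Specific Aims predicts that the 6-month difference will widen by 12 months, but no planned contrast tests widening, and the default straight-line model fixes the 12-month difference at twice the 6-month one

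*Combined protocol and SAP*

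**What the plan says.** The two statements of the Aim 1 prediction differ. Specific Aims expects QOL and caregiver burden to be better with palliative care "at 6 months and that this difference will persist and widen by 12 months". Approach, Aim 1, Rationale and Design has "at 6 months and that this difference will persist at 12 months", with no mention of widening.

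Aim 1, Statistical Analysis lists as main contrasts the difference in area under the change-from-baseline curves and the between-arm difference in change at 6 months. It then adds: "Secondary tests will be conducted for the mean difference in change from baseline between the groups at the 3, 9, and 12-month time points". The time-by-treatment interaction is also to be tested.

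On the form of the model: "The default model will have linear time trajectories for each treatment group", and "If the time trajectories are linear, then all tests are stochastically equivalent to the time by treatment interaction test with one parameter". On the safeguard: "The linearity assumptions will be checked". Piecewise linear functions or transforms are offered as an option if the trend is not linear. No test, threshold or rule for switching is stated. The Aim 3 power section adds that linear time functions make comparisons at separate time points unnecessary.

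**The concern.** Write Dk for the between-arm difference in change from baseline at month k, signed so that a positive value favours palliative care. Persistence concerns whether D12 exceeds zero. Widening concerns whether D12 exceeds D6, so its null is D12 = D6. The planned 12-month test has the null D12 = 0, which will tend to be rejected while a useful benefit is still present, whether it has grown, held or partly faded. Nothing else listed isolates month 12 against month 6.

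The default model makes this harder to see. With one straight line per arm, Dk = k × (slope difference), so D12 = 2 × D6 whatever the data show, with the same p-value. Once the slope favours palliative care, the widening prediction cannot be contradicted.

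What is at stake is whether the benefit of a care model that the protocol itself calls time- and resource-intensive grows, holds or fades after six months. The 6-month estimate, a main contrast, is also at stake, because a straight line forced through a plateau pulls it down.

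**Working it through.** **Inputs.** From Aim 1, Sample Size and Power Considerations: 125 per arm after dropout to month 6, 90 dyads per arm as the minimum for caregiver outcomes, compound symmetry with ρ = 0.5, a common intercept, and effects of 0.36 and 0.42 SD. Visits are at 0, 3, 6, 9 and 12 months. Assumptions of this check: two-sided alpha 0.05, normal approximation, and 90 to 125 per arm still present at month 12, because no 12-month dropout is given.

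**Reproducing the plan's figure.** With a knot at each visit, Var(D6) = 2(1 − ρ²)/n = 1.5/n. The detectable effect at 90% power is (1.960 + 1.282) × √(1.5/125) = 0.355 SD; the plan states 36%. The same formula gives 0.418 SD for 90 per arm (plan: 42%) and 0.496 SD for 64 per arm (plan: 50%).

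**What the straight line estimates.** The four visit differences (D3, D6, D9, D12) have covariance (I + 0.5J)/n, where J is the matrix of ones, with inverse n(I − J/6). With x = (3, 6, 9, 12), the fitted slope is (−2·D3 + D6 + 4·D9 + 7·D12)/120, with variance 1/(120n). So:

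- fitted D12 = −0.2·D3 + 0.1·D6 + 0.4·D9 + 0.7·D12, and fitted D6 is half of that;
- SE of fitted D12 = 12/√(120 × 125) = 0.098 SD, against √(1.5/125) = 0.110 SD with categorical time.

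For a true plateau of 0.36 SD:

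- from month 3 (0.36 at every visit): fitted D12 = 0.36 × 1.0 = 0.360 and fitted D6 = 0.180;
- from month 6 (0.18, 0.36, 0.36, 0.36): fitted D12 = 0.36 × 1.1 = 0.396 and fitted D6 = 0.198.

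**How often the doubled result survives a linearity check.** The plan names no check. Assume a 3-df test, at 5%, of treatment by non-linear time. Its non-centrality is n·D²·c, where c = 0.5 for a plateau from month 3 and c = 0.2 for a plateau from month 6. For D = 0.36 and n = 125 this is 8.10 and 3.24. The slope estimate and the lack-of-fit statistic are independent, so P(significant and undetected) = P(significant) × (1 − P(detected)).

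| Plateau from | D (SD) | n per arm | P(significant) | P(misfit detected) | Significant, doubled, undetected |
|---|---|---|---|---|---|
| month 3 | 0.36 | 125 | 0.957 | 0.660 | 33% |
| month 3 | 0.42 | 125 | 0.990 | 0.805 | 19% |
| month 6 | 0.36 | 125 | 0.981 | 0.295 | 69% |
| month 6 | 0.42 | 125 | 0.997 | 0.393 | 61% |
| month 3 | 0.36 | 90 | 0.877 | 0.505 | 43% |
| month 3 | 0.42 | 90 | 0.953 | 0.650 | 33% |
| month 6 | 0.36 | 90 | 0.929 | 0.219 | 73% |
| month 6 | 0.42 | 90 | 0.979 | 0.289 | 70% |

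**Fading.** If the true profile is 0.18, 0.36, 0.27, 0.18 SD, fitted D12 = 0.36 × 0.65 = 0.23 SD and fitted D6 = 0.12 SD. With 125 per arm this is significant in 67% of trials, and significant with the misfit undetected in about 26%.

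**Separate intercepts.** The analysis section does not say whether the arms share an intercept. If they do not, a 0.36 SD plateau from month 3 is fitted as 0.144 SD at month 6 and 0.288 SD at month 12. The ratio is still two.

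**The direct contrast.** Var(D12 − D6) = 4(1 − ρ)/n = 2/n, so SE = √(2/125) = 0.126 SD. Under a flat benefit it points falsely to widening in 2.5% of trials. If the difference grows from 0.36 to 0.72 SD, power is Φ(0.36/0.1265 − 1.96) = 81%. With 90 per arm, SE = 0.149 SD and power is 68%.

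**The case against.** A reader might infer that the plan commits the sponsor to calling a significant 12-month test widening, so that a flat benefit would be misreported with high probability. The documents do not support that. No section says the 12-month result will be used as evidence of widening. The word appears in one predictive sentence of Specific Aims, and the fuller design text drops it. The 12-month tests are labelled secondary, and for persistence a test of D12 against zero is adequate when time is modelled flexibly.

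Nor is it an error that, with categorical time and a flat 0.36 SD, the 12-month test rejects in 91% of trials. That is correct power for a benefit truly present at month 12. The estimates and 95% CIs that the plan promises would let a reader see a flat profile under that model.

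The linearity check is also a real safeguard in some cases. For a plateau starting at month 3 the assumed check finds the misfit in 66% (0.36 SD) or 81% (0.42 SD) of trials with 125 per arm. It is much weaker for a plateau starting at month 6. If the trajectories truly are linear, the interaction test does test widening, since D12 − D6 = 6 × the slope difference, and the plan openly says its tests then coincide.

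These points limit the claim to a conditional one. They do not supply a contrast for widening, nor a rule for leaving the straight line. Relying on the interaction test for widening also presumes the linear shape that is in question.

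**Conclusion.** The point holds in conditional form. Specific Aims makes a prediction that no listed contrast tests, and the Approach section makes a weaker one. The default model fixes the ratio of the 12-month to the 6-month difference at two. If it is kept, a benefit that plateaus or partly fades could be reported as doubling.

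For a flat benefit of 0.36 to 0.42 SD, the chance of a significant, doubled and undetected result is about 19–33% (plateau from month 3) or 61–69% (plateau from month 6) with 125 per arm, and 33–43% or 70–73% with 90 dyads per arm. These figures rest on the plan's covariance assumptions, a common baseline, full retention of those numbers to month 12, and a check that this review had to assume.

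The automatic doubling should not be read as inflation at month 12. With a common baseline and a true plateau of 0.36 SD, the 12-month estimate is about right or 10% high (0.36–0.40 SD). The main harm is to the 6-month main contrast, estimated at 0.18–0.20 SD. The widening prediction is secondary, but the correction is cheap and also protects a main contrast, so it should be made.

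**What to change.** In Aim 1, Statistical Analysis:

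- Estimate the visit-specific differences for QOL-AD and ZBI from a model with categorical time or a knot at each visit. The power section already uses the knot-per-visit form.
- Add D12 − D6 for each scale with its 95% CI. Claim widening only if that interval excludes zero in favour of palliative care, and judge persistence from D12 in the same model.
- State that the straight-line 12-month estimate is not evidence of widening.

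Make the predictions in Specific Aims and in Approach, Rationale and Design the same. If the new contrast is judged underpowered, drop the widening prediction from Specific Aims.

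The cost is wording and one extra contrast per scale from data already collected. The 12-month estimate is slightly less precise (SE 0.110 against 0.098 SD with 125 per arm), and a widening claim becomes harder to make: 81% power for growth from 0.36 to 0.72 SD with 125 per arm at month 12, and 68% with 90. The plan should state the 12-month retention it expects, since the documents give none.

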Unified Parkinson Disease Rating Scale ⁴¹	Patient Motor symptom Severity (motor exam only)
Montreal Cognitive Assessment (MOCA) ^{46, 56}	Patient Cognitive Status
Hoehn and Yahr Scale ⁴⁴	Patient Disease Stage (baseline visit only)
Charlson Comorbidity Index ^{61, 66}	Medical Comorbidities (baseline visit only)

Statistical Analysis: The main objective of the study is to determine the comparative effectiveness of interdisciplinary outpatient palliative care versus usual care with a neurologist for PD regarding effects on patient QOL and caregiver burden. The primary outcome variables will be the QOL-AD and the ZBI.^{40, 55} Secondary outcomes (see **Table 2**) include scales for symptom burden, mood, and spiritual wellbeing. Controlling covariates will include gender, age, disease severity (measured continuously using the Unified Parkinson Disease Rating Scale⁶⁷), cognitive dysfunction (measured continuously using the Montreal Cognitive Assessment⁶⁸), and baseline depression (measured continuously using the HADS Depression Subscale⁶⁴). The explanatory variables will be checked for randomization and multicollinearity. Successful randomization should minimize covariate imbalances between groups, but including them in the model can adjust for lingering confounding effects and account for variance in the outcome variable.

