from models using all available data for a response variable will be compared to the models with missing data methods. The random effects linking together the joint models will be tested. The missing data methods assume missing at random (MAR). Randomization will be checked for baseline variables with summary statistics and two-way tables. Covariates can partially control for deviations from ideal randomization. Homoskedascity and approximate normality for the outcomes will be checked with standard methods. Homoskedascity can be remedied with heterogeneous variance structures or weights. Non-normality should not be much of an issue, unless severe, and can be dealt with using standard methods such as logarithmic transformations. With our sample size the parameter estimates should be consistent and asymptotically normal because of the Central Limit Theorem. All variables will be checked for outliers, and influential outliers will be considered for removal using standard tests (e.g. Cook's D).

Sample Size and Power Considerations: Allowing for up to 25 dropouts per group by the 6-month time point, a two sample T-test with 125 samples per treatment group (250 total) will detect a difference in our continuous outcomes equal to 42% of the standard deviation with 90% power and an alpha level 0.05. This is greater than the suggested minimal clinically significant change for the QOL-AD of 3 points.⁷⁰ For our secondary measure of QOL the difference of half the standard deviation for the PDQ-39 has been suggested in prior studies to be clinically important and detectable with change over time or with outpatient interventions.^{63, 71, 72} For the ZBI, assuming 110 complete dyads per group would diminish our effect size to 44% of the standard deviation with 90% power and an alpha level 0.05. Even a sample of 90 complete dyads would provide an effect size of 0.5 SD/mean. Minimal clinically important differences have not been established for the ZBI but will be estimated in this study using caregiver global impression of improvement and an anchor based approach.⁷³ Notably, prior studies of palliative interventions have found effect sizes of 0.5 SD/mean and greater for the ZBI.¹⁹ The sample size will also enable us to fit models with a large number of parameters and as described below, the longitudinal mixed models and linear time functions will increase our efficiency. Caregivers will be enrolled for each part

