5) *Will results be biased without blinding?* It is impossible to truly blind an intervention of this nature. We have used patient-reported outcomes to increase the relevance of results as there are no objective biomarkers relevant to our research questions. Despite this, prior multidisciplinary and palliative intervention trials have reported negative results suggesting that blinding biases do not overwhelm clinical effects.⁴⁴

Future Directions

If this intervention is successful in improving patient QOL and/or caregiver distress we would plan to explore alternate delivery methods to improve the efficiency and dissemination of this approach including telemedicine, group visits, smaller teams and mixed approaches (e.g. in person physician visit and telehealth counseling). Cost-effectiveness studies would also be an important follow-up question to influence system level decisions for this model of care. Lastly, application to other progressive neurological illnesses, including mixed populations, may be warranted as patients with advanced chronic neurological illness tend to be similar in terms of symptoms and needs.

If this intervention is not successful, future studies would be guided by the results of Aim 3. Benefits found in specific subgroups would suggest a need for the development of better screening instruments, while poor responses across the sample would suggest a need for a different model. High drop-out rates or noncompliance with the intervention would suggest a need for alternate delivery methods.

HUMAN SUBJECTS

1. Risks to Human Subjects

1.a. Human Subjects Involvement, Characteristics and Design

Due to the nature of our research questions regarding clinical, psychosocial and spiritual needs in PD patients and their family caregivers we feel that involvement of human research subjects is necessary and justified. As we will discuss below, the risks of this research to human subjects are minimal and the potential for benefit for the involved human subjects, other people and family members living with PD, and society is significant.

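### Aim 1 tests two primary outcomes at 0.05 each with no success rule or committed error control; if either win counts, the false-rejection rate is about 8–10%

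*Combined protocol and SAP*

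**What the plan says.** All references are to the combined protocol and SAP.

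- **Outcomes.** Aim 1, Statistical Analysis: "The primary outcome variables will be the QOL-AD and the ZBI". Primary Outcome Measures agrees.
- **Significance level.** Same section: "The contrasts, controlled for all covariates, will be tested for significance using T-tests and F-tests, with an alpha level of 0.05". No division of alpha between the outcomes is given.
- **Power.** Aim 1, Sample Size and Power Considerations uses alpha 0.05 for each. With 125 patients per group, a t-test "will detect a difference in our continuous outcomes equal to 42% of the standard deviation with 90% power". For the ZBI, 110 complete dyads per group "would diminish our effect size to 44% of the standard deviation with 90% power and an alpha level 0.05".
- **Claim worded as and/or.** The Aim 1 heading under APPROACH asks whether palliative care "improves patient quality of life (QOL) and/or caregiver burden versus usual care". Future Directions opens with "If this intervention is successful in improving patient QOL and/or caregiver distress".
- **Claim worded as and.** Specific Aims, Aim 1: "Our primary outcomes will be differences between groups in patient QOL and caregiver burden at 6 months". The prediction in Aim 1, Rationale and Design is that "patient QOL and caregiver burden will be significantly improved in the palliative care group versus usual care at 6 months".
- **Multiplicity.** The Aim 1 power section notes that Bonferroni is available and that the 6-month test would keep its power after correction for nearly 50 tests. It neither commits to a correction nor names the family of tests. The remarks on multiple comparisons under Aim 3 concern the interaction analyses.
- **Contrasts.** Statistical Analysis names two main contrasts per outcome, the area under the change curve and the 6-month change, and does not say which decides. It adds that they are equivalent if trajectories are linear, which is the default model.
- **A wording conflict.** One sentence in Aim 1, Rationale and Design gives symptom burden as a primary outcome in place of QOL. The same paragraph then lists symptom burden as secondary.

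**The concern.** Three success rules fit the text, and they have different consequences.

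1. **Either outcome suffices.** Testing each at 0.05 does not hold 5% for the Aim 1 claim.
2. **Both are required.** There is no inflation, but power for the claim is below the 90% quoted for each outcome.
3. **Two separate claims, one for patients and one for caregivers.** Testing each at 0.05 can stand, but only if the plan says that this is what is meant and does not merge the two into one statement of success.

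As written, the choice among these could be made after the results are known.

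**Working it through.** **Inputs.** Two primary outcomes; alpha 0.05 per test; 125 per group at 0.42 SD (QOL-AD); 110 dyads per group at 0.44 SD (ZBI); for the longitudinal figures, compound symmetry with correlation 0.5. All are from Aim 1, Statistical Analysis and Sample Size. The correlation between the two outcomes' test statistics is not given; I assume 0 to 0.7, with benefit scored positive on both.

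**1. The plan's own figures.** Noncentral t, two-sided 0.05: 125 per group at 0.42 SD gives 91.1%; 110 per group at 0.44 SD gives 90.1%. One-sided tests would give about 95%, so the plan's tests are two-sided. For the 6-month change, with variance 1 − 0.5² = 0.75, the difference detectable with 90% power is (1.960 + 1.282) × √(1.5/n) = 0.355 SD for n = 125 and 0.419 SD for n = 90, matching the stated 36% and 42%. At 0.5 SD and n = 125, power at 0.05/49 is 90.0%, which reproduces the statement about nearly 50 tests.

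**2. Either outcome suffices.** Probability of at least one false rejection = 1 − P(|Z₁| ≤ 1.96 and |Z₂| ≤ 1.96). At correlation 0 this is 1 − 0.95² = 9.75%. False benefit on at least one outcome is 1 − 0.975² = 4.94%. For other correlations, bivariate normal integration; Holm false benefit by simulation:

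| Correlation | Any false rejection | False benefit | Holm, any | Holm, benefit |
|---|---|---|---|---|
| 0 | 9.75% | 4.94% | 4.94% | 2.5% |
| 0.3 | 9.51% | 4.76% | 4.84% | 2.4% |
| 0.5 | 9.07% | 4.54% | 4.65% | 2.3% |
| 0.7 | 8.35% | 4.17% | 4.30% | 2.1% |

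**3. Both required.** Under the normal approximation the single-outcome powers are 91.3% and 90.4%. Joint power at correlation 0 is 0.913 × 0.904 = 82.5%; at 0.3, 0.5 and 0.7 it is 83.6%, 84.5% and 85.9%.

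**4. Two main contrasts.** Under the default linear model these are one test, so step 2 stands. Only if a piecewise model is used and either contrast may count are there four tests. Take the trapezoid area over 0–12 months with a common baseline: variance of area 42.1875, variance of 6-month change 0.75, covariance 4.125, so the correlation is 4.125/√(42.1875 × 0.75) = 0.733. Assume further that the correlation between one outcome's area and the other's 6-month change is the product of the two correlations. Any false rejection is then 15.7% to 13.4% for outcome correlation 0 to 0.7 (simulation). With simple change scores the contrast correlation is 0.808 and the range is 14.9% to 12.7%.

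**The case against.** The strongest reply is that the 8–10% belongs to one of three readings. QOL-AD concerns the patient and ZBI the caregiver; they have different denominators and separate power statements, and an estimate, interval and p value will be reported for each contrast. That supports two separate claims, for which 0.05 each is defensible. The and/or texts are an aim heading and a paragraph on follow-up research, not decision rules, and the explicit predictions say and. This stands as far as it goes: what is shown is a missing rule, and the inflation is conditional on the either-win reading. But Future Directions is the nearest the plan comes to defining success, and it joins the two outcomes with and/or.

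A second reply is that multiplicity was considered. It was, and at 0.5 SD the power section shows ample room for a correction. But an optional correction with no named family controls nothing.

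Third, the four-test figure needs a non-linear model, an either-contrast rule and a further correlation assumption. Specific Aims and Aim 1, Rationale and Design set the primary comparison at 6 months, which points away from the either-contrast rule. The figure is a side note only.

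The symptom-burden sentence is a drafting slip that adds nothing to the error-rate argument, though it does contradict the list of primary outcomes.

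**Conclusion.** The concern holds and should be fixed. The plan has two primary outcomes, each tested at 0.05, with no success rule and no committed error control. The missing rule is a defect whatever the correlation between outcomes. Under the and/or reading, at least one false rejection occurs in 8.4–9.8% of trials with no true effect, and a false benefit in 4.2–4.9%, assuming a correlation of 0 to 0.7 and one deciding contrast per outcome. Under the both-required reading the error rate is not inflated, but power for the claim is 83–86% at the plan's own effect sizes. Under two separate claims, 0.05 each is acceptable once declared.

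**What to change.** 1. In Aim 1, Statistical Analysis, make the 6-month change from baseline the sole primary contrast, and move the area contrast to secondary alongside the 3-, 9- and 12-month contrasts. A fixed testing order for the two main contrasts would also work.
2. State one success rule. To fit the and/or wording:
   > Aim 1 is met if QOL-AD or ZBI shows a significant benefit at 6 months; the two are tested by Holm's procedure at an overall two-sided 0.05.

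   If both are to be required, say so; no adjustment across the outcomes is then needed, and joint power should be reported. If two separate claims are intended, declare them, each at 0.05, with no combined statement of success.
3. Use the same wording of the claim in Specific Aims, the Aim 1 section under APPROACH, and Future Directions.
4. In Aim 1, Rationale and Design, replace symptom burden as a primary outcome with patient QOL (QOL-AD).

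**Cost.** Wording only; no added patients. Holm's worst case is that an outcome must pass at 0.025:

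| Basis | Power at 0.05 → 0.025 | 90%-power difference at 0.025 |
|---|---|---|
| t-test, 125 per group, 0.42 SD | 91.1% → 85.6% | 0.448 SD |
| t-test, 110 dyads per group, 0.44 SD | 90.1% → 84.2% | 0.478 SD |

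If both planned effects are real, Holm keeps about 89–91% power for QOL-AD and 88–90% for ZBI. On the longitudinal basis, (2.241 + 1.282) × √(1.5/n) gives 0.386 SD for 125 per group (from the stated 0.36) and 0.455 SD for 90 dyads per group (from 0.42). At 0.5 SD with 125 per group, power at 0.025 is still 99%.
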